2.5.1. Phase I/II Clinical Study (APR-246-01, dose de-escalation)

This was a multi-center, open label, non-comparative, phase I, dose de-escalating study of APR-246 infusions in patients with refractory hematologic malignancies. In this study (Amendment No. 6) a longer infusion time was applied resulting in an increased exposure of APR-246²⁸. In Amendment No. 6, the objective was to increase the knowledge of the optimal way to administer APR-246 and study the safety and tolerability as well as the pharmacokinetic (PK) profile of APR-246. Ten patients with acute myeloid leukemia (AML) or chronic lymphocytic leukemia (CLL) were planned for enrolment. The treatment schedule was 4 consecutive days with APR-246 with the modified dosing regimen of a start boosting infusion of 50 mg/kg during 45 min, followed by an 85 mg/kg infusion for 5.15 hours. If toxicity was shown, the dose was to be decreased to Dose level 2 (45 mg/kg for 45 min [infusion rate 60 mg/kg/h], followed by 60 mg/kg [infusion rate 10 mg/kg/h] for 5.15 hours), on the discretion of the investigator and/or the Study Board. Out of the 2 AML patients with *TP53* mutation, both had a blast reduction, one constituting a response according to the response criterion²⁸. On the lower dose of 67.5mg/kg, there were no DLTs or SAEs. Overall in this study there were 6/10 patients treated at 67.5 mg/kg or higher with no or only mild side effects supporting the 67.5mg/kg dose as the HFD and recommended for further development.

The pharmacokinetics was studied at selected time points during the treatment and the data

showed that no accumulation of APR-246 was observed after four daily doses or after 3 cycles. Plasma clearance and volume of distribution were comparable between Day 1 and Day 4, suggesting a time-independent kinetics. The PK parameters obtained in the present study, were also in line with the previous single dose study (2-90 mg/kg, 2 h infusion) and linear kinetics could be concluded for APR-246 up to 135 mg/kg. Several patients tolerated the mid-dose, 105 mg/kg treatment, where the C_{max} was in the range of 45-85 µg/mL with an exposure up to 860 µg*h/mL (AUC_{0-24h}), whereas one patient withdrew having the highest exposure (1060 µg*h/mL) in the whole study. The results of the extension study of APR-246 in patients with AML and CLL suggest that the dose regimen with HFD of 67.5 mg/kg given as a 6-hour bi-phasic infusion was suitable and that APR-246 was well tolerated with limited number of AEs reported. The pharmacokinetic data suggested time-independent and dose-independent kinetics. In the patients, plasma concentrations consistently above those associated with effects in both ex vivo and in vivo pre-clinical models have been achieved. Four patients showed signs of response and 2 of them were responders according to the definition in the protocol. A response was observed in 4 of the 5 patients carrying mutant *TP53*. The effect of APR-246 on tumor burden and apoptosis markers indicates beneficial effects. Given the critical unmet need for treatment of *TP53* mutant MDS and AML patients, we propose this phase Ib/II study.

2.5.2. APR-246 in advanced ovarian cancer

A 2-part study has been designed (APR-407) in women with advanced high grade serous ovarian cancer (HGSCO) given APR-246 in combination with carboplatin and pegylated liposomal — doxorubicin (PLD). This is based on the fact that >90% of HGSC are *TP53* mutant and *in vitro* and *in vivo* data suggesting synergism with platinum agents²⁸. The APR-407 Phase Ib portion is nearly completed in the European Union and the recommended Phase II dose of 67.5 mg/kg (corresponding to 100 mg/kg lean body mass (LBM)) has been confirmed based upon assessment of cumulative safety data from the Phase Ib. Currently, additional patients are being enrolled in Phase Ib expansion cohort to collect additional safety and cardiac QTc and PK data at the Phase II dose (100 mg/kg LBM); the target is to have matched ECG and PK data from 20 patients at the Phase II dose. The APR-407 Phase II portion will open to accrual in the EU after regulatory clearance, and in the US pending IND activation. A summary of the adverse events seen in this protocol are detailed below.

[REDACTED]

[REDACTED]

[Redacted text block consisting of approximately 18 lines of blacked-out content]

[REDACTED]

- 1 [REDACTED]
- 2 [REDACTED]
- 3 [REDACTED]

[REDACTED]

[REDACTED]

[REDACTED]

[REDACTED]

[REDACTED]

[REDACTED]

[REDACTED]

[REDACTED]

[REDACTED]

[REDACTED]

[REDACTED]

[REDACTED]

[REDACTED]

[REDACTED]

[REDACTED]

[REDACTED]

[REDACTED]

[REDACTED]

[REDACTED]

[REDACTED]

[REDACTED]

[REDACTED]

[REDACTED]

[Redacted text block]

[Redacted text block]

[Redacted text block]

[REDACTED]

[Redacted text block]

[Redacted text block]

[Redacted text block]

[Redacted text block]

[Redacted text block]

[REDACTED]

[REDACTED]

[REDACTED]

[REDACTED]

[REDACTED]

[REDACTED]

[REDACTED]

3. STUDY ENDPOINTS

3.1. Primary

3.1.1. Phase 1b: DLTs occurring in the first 2 cycles (8 weeks), as defined below, graded according to the National Cancer Institute Common Terminology Criteria for Adverse Events (NCI CTCAE), Version 4.03

3.1.2. Phase 2: CR rate by IWG 2006 criteria (appendix B)

3.2. Secondary

3.2.1. Duration of response defined as the time between achieving response and progression of

disease.

3.2.2. OS at 8 months

3.2.3. Proportion of subjects achieving hematological improvement (HI), partial response (PR), complete response (CR), and/or marrow CR (mCR) by the IWG 2006 criteria (see appendix B)

3.2.4. Proportion of subjects who obtain a response as defined by IWG 2006 criteria with a baseline *TP53* VAF $\geq 20\%$ versus $< 20\%$

3.2.5. Proportion of subjects who achieve $\geq 50\%$ reduction in *TP53* VAF.

3.2.6. Progression free survival (PFS) and OS in clonal responders ($\geq 50\%$ reduction in *TP53* VAF) versus non-responders

3.2.7. To determine expression of genes related to p53-mediated signal transduction before and after APR-246 treatment

3.2.8. To determine ROS production before and after APR-246 treatment

3.2.9. AML transformation according to World Health Organization (WHO) criteria

3.2.10. OS

3.2.11. LFS

3.2.12. Determine recurrent gene mutations in *ASXL1*, *BCOR*, *BRAF*, *CALR*, *CBL*, *CEBPA*, *CSF3R*, *DNMT3A*, *ETV6*, *EZH2*, *GATA2*, *GNAS*, *IDH1*, *IDH2*, *JAK2*, *KIT*, *KRAS*, *MPL*, *NF1*, *NPM1*, *NRAS*, *PDGFRA*, *PDGFRB*, *PHF6*, *PTPN11*, *RAD21*, *RUNX1*, *SETBP1*, *SF3B1*, *SMC1A*, *SMC3*, *SRSF2*, *STAG2*, *STAT3*, *STAT5b*, *TET2*, *TP53*, *U2AF1*, *WT1*, and *ZRSR2* at study entry and serially throughout treatment to assess changes in somatic mutation landscape

4. PATIENT SELECTION

4.1. Eligibility criteria

Inclusion Criteria:

1. Patient has signed the Informed Consent (ICF) and is able to comply with protocol requirements
2. Patient has adequate organ function as defined by the following laboratory values:
 - a. Serum creatinine ≤ 2 x upper limit of normal (ULN)
 - b. Total serum bilirubin < 1.5 x ULN or total bilirubin ≤ 3.0 x ULN with direct bilirubin within normal range in patients with well documented Gilbert's Syndrome or

hemolysis or who required regular blood transfusions

- c. Alanine aminotransferase (ALT) and aspartate aminotransferase (AST) $< 2.5 \times \text{ULN}$
3. Age ≥ 18 years at the time of signing the informed consent form
4. Documented diagnosis of myelodysplastic syndrome (MDS), MDS/ myeloproliferative neoplasm (MPN), chronic myelomonocytic leukemia (CMML) by WHO criteria or AML with 20-30% myeloblasts (refractory anemia with excess blasts in transformation (RAEB-T) by French-American-British (FAB) criteria)
5. Documentation of a *TP53* gene mutation by NGS based on central or local evaluation
6. Revised International Prognostic Scoring System (IPSS-R) criteria for Intermediate, High-risk or Very High-risk.
7. An Eastern Cooperative Oncology Group (ECOG) performance status score of 0, 1, or 2 is required.
8. If of childbearing potential, negative pre-treatment urine or serum pregnancy test.
9. If of childbearing potential (males and females), willing to use an effective form of contraception such as latex condom, hormonal birth control, intrauterine device or double barrier method during chemotherapy treatment and for at least six months thereafter.

Exclusion Criteria

1. Patient has a known history of HIV or active hepatitis B or active hepatitis C infection (testing not mandatory).
2. Patient has any of the following cardiac abnormalities (as determined by treating MD):
 - a. Symptomatic congestive heart failure
 - b. Myocardial infarction ≤ 6 months prior to enrollment
 - c. Unstable angina pectoris
 - d. Serious uncontrolled cardiac arrhythmia
 - e. QTc ≥ 470 msec
3. Concomitant malignancies or previous malignancies with less than a 1-year disease free interval at the time of signing consent. Patients with adequately resected basal or squamous cell carcinoma of the skin, or adequately resected carcinoma in situ (e.g. cervix) may enroll irrespective of the time of diagnosis.
4. Prior exposure to azacitidine, decitabine or investigational hypomethylating agent.
5. Use of cytotoxic chemotherapeutic agents, or experimental agents (agents that are not

commercially available) for the treatment of MDS, MDS/MPN, CMML or AML within 14 days of the first day of study drug treatment.

6. No concurrent use of erythroid stimulating agents, G-CSF, GM-CSF is allowed during study except in cases of febrile neutropenia where G-CSF can be used for short term. Growth factors must be stopped 14 days prior to study.
7. Patients with history of allogeneic stem cell transplantation.
8. Pregnant women are excluded from this study because APR-246 has not been studied in pregnant subjects. Because there is an unknown but potential risk for adverse events in nursing infants secondary to treatment of the mother with APR-246, breastfeeding should be discontinued if the mother is treated with APR-246.

4.2 Inclusion of Women and Minorities

Both men and women and members of all races and ethnic groups are eligible for this trial.

5. STUDY DESIGN

This study will be a multi-institution, open-label, phase Ib/II clinical trial conducted in 2 parts: a Phase 1b part followed by a Simon's two-stage Phase 2 design. The study will assess the safety and efficacy of APR-246 in combination with azacitidine for the treatment of *TP53* mutant myeloid neoplasms. All patients will have pre-screening NGS on peripheral blood (PB) or bone marrow (BM) samples to determine *TP53* mutational status and therefore eligibility to participate in this study. A PB sample will be obtained prior to treatment for NGS by the central laboratory to evaluate baseline *TP53* VAF and for serial analysis.

6. TREATMENT PLAN

a. APR-246 administration

Treatment will be administered on an outpatient basis. Reported adverse events and potential risks are described in Section 11. Appropriate dose modifications for APR-246 are described in Section 10. No investigational or commercial agents or therapies other than those described below may be administered with the intent to treat the patient's MDS or MDS/MPN. APR-246 will be supplied by Aprea.

Phase 1b Part:

The initial Phase 1b part will evaluate APR-246 administered with azacitidine. Cohorts of at least 3 evaluable patients will be enrolled using a modified 3 + 3 design. Patients will receive IV infusions of APR-246 as a lead-in phase on days -14 to -11 starting at Dose Level 1 (see Table 5) prior to starting cycle #1 of combination therapy with azacitidine (see Figure 2). In all cycles, APR-246 will be administered as a 6-hour infusion daily for four consecutive days (study days -14 to -11 of the lead in phase and day 1 to 4 of each combination cycle). **The entire dose should be given even if the infusion needs to be extended beyond a total time of six hours (e.g., due to slightly larger start volume in prefilled infusion bags).**

- Dose Level 1 (Starting dose): APR-246 21.0 mg/kg LBW (for first 45mins) + 29 mg/kg LBW (for 5hrs 15mins) on Days 1 to 4
- Dose Level 2: APR-246 30.0 mg/kg LBW (for first 45mins) + 45.0 mg/kg LBW (for 5hrs 15mins) on Days 1 to 4
- Dose Level 3: APR-246 37.0 mg/kg LBW (for first 45mins) + 63.0 mg/kg LBW (for 5hrs 15mins) on Days 1 to 4

[figure not shown]

Figure 2. Dosing schedule for Phase 1b/2 investigation of APR-246 in combination with azacitidine

Combination therapy will consist of APR-246 on days 1-4 and azacitidine on days 4-10 of a 28 day cycle. Azacitidine will be administered subcutaneously (SC) or IV (SC preferred) at 75mg/m² for 7 days (either 7 consecutive days (days 4-10) or 2+5 (i.e., days 4-5 and 8-12)). Azacitidine will be administered on day 4 at the same time as the final infusion of APR-246. Azacitidine administration will occur following the completion of APR-246 infusion. Patients

Phase 2 Starting Dose Level (DL)	APR-246 4.5 g/patient/day 1.5 g/patient (for first 45 minutes) + 3.0 g/patient (for 5 hours 15 minutes)
First dose reduction DL-1	APR-246 4.0 g/patient/day 1.33 g/patient (for first 45 minutes) + 2.67 g/patient (for 5 hours 15 minutes)
Second dose DL-2*	APR-246 3.5 g/patient/day 1.16 g/patient (for first 45 minutes) + 2.34 g/patient (for 5 hours 15 minutes)

A Simon’s two-stage minimax design will be applied, as follows:

Stage 1: Enroll a total of 24 evaluable patients at the MTD (including patients who were enrolled during the Phase 1 part of the study). If less than 6 of 24 patients achieve CR, then the study will be terminated early with the conclusion that the regimen does not warrant further investigation. If 6 or more patients achieve CR, then enrollment will be permitted to continue to Stage 2.

Stage 2: Enroll 21 more evaluable patients for a total of 45. If less than 14 of 45 patients achieve CR, then there is insufficient evidence to support continued study of this treatment. If 14 of 45 patients achieve CR, then there is sufficient evidence to support further study of APR-246 in combination with azacitidine in Phase 3. Up to 39 additional evaluable patients will be treated at the level of the MTD in the Phase 2 portion of the trial. The maximum total accrual is 51 patients. Disease assessments will occur following 3 cycles of therapy (Figure 3).

[figure not shown]

Figure 3. Phase 2 Schema

b. General Concomitant Medication and Supportive Care Guidelines

In general, the use of any concomitant medications/therapies deemed necessary for the care of the patient are allowed, with specific exceptions below. Prophylactic anti-emetic therapy is permitted where indicated.

Any disease progression that requires other specific anti-tumor therapy will be cause for discontinuation from the trial.

c. Permitted Medications

i. Growth Factors

Erythropoiesis-stimulating agents (ESAs) are not allowed for anemia during the study. G-CSF is allowed during study only in cases of febrile neutropenia where G-CSF can be used for short term.

ii. Anticoagulant Therapy

Subjects who are taking warfarin (or equivalent) may participate in this study; however, it is recommended that prothrombin time (PT-INR) and PTT be monitored carefully at least once per week for the first month, then monthly if the INR is stable. Subcutaneous heparin, low molecular weight heparin and oral anticoagulants are permitted.

iii. QT prolonging Agents

[REDACTED]

[REDACTED]

[REDACTED]

Other investigational therapies must not be used while the patient is on the study.

7. Duration of Therapy

Subjects will be treated for a total of 6 cycles. For subjects who have stable disease or better, treatment may continue until one of the following criteria applies:

- e. Inter-current illness that prevents further administration of treatment,
 - f. Unacceptable adverse event(s),
 - g. Patient decides to withdraw from the study, or
 - h. General or specific changes in the patient's condition render the patient unacceptable for further treatment in the judgment of the investigator.
- e. Evidence of disease progression by the IWG 2006 criteria, not applicable at bone marrow evaluation at day -10 of lead in phase.

Subjects who wish not to continue treatment will complete their end of study visit upon completion of cycle 6.

8. Duration of Follow-Up

Subjects will be followed as per calendar on treatment for 6 cycles. After 6 cycles, patients who continue on treatment will be followed monthly. Off treatment data on AML transformation and overall survival will be updated every 6 months or until death, whichever occurs first. Subjects removed from study for unacceptable adverse events will be followed until resolution or stabilization of the adverse event.

9. Criteria for Removal from Study

a. Subject Completion

A subject will be considered to have completed the study if the subject meets at least 1 of the following criteria:

- The subject has progressive disease.
- The subject died during the study.
- The subject experience a treatment related AE that led to withdrawal from the study.
- The subject starts new treatment for their underlying disease (MDS/CMML/AML).

b. Subject Withdrawal from Study

A subject may voluntarily withdraw from study medication or withdraw consent from the study at any time. The investigator may also, at his or her discretion, discontinue a subject from participating in the study at any time. The investigator and/or designated staff will record the date and the reason for subject withdrawal from the study.

c. Subject Withdrawal from Study Medication

If the subject is permanently withdrawn from treatment with study medication, but does not withdraw consent, the investigator must make every effort to have the subject complete all withdrawal assessments at the time of withdrawal, and complete all scheduled follow-up visits.

Treatment with study medication must be discontinued if:

- The subject withdraws consent.
- Further participation would be injurious to the subject's health or well-being in the investigator's medical judgment.
- The study is terminated.
- The subject becomes pregnant.
- Evidence of disease progression according to IWG 2006 criteria (see Appendix B, not applicable at bone marrow evaluation at day -10 of lead in phase).
- A subject is significantly non-compliant with the requirements of the protocol.
- A subject has an adverse experience that would, in the investigator's judgment, make continued participation in the study an unacceptable risk.

d. Study safety-related stopping rules

In the following conditions, the study may be temporarily or permanently stopped, pending review by the Steering Committee and the Sponsor:

1. Patient death due to APR-246. If there is Grade 5 toxicity definitely or probably attributed to study treatment within 28 days of APR-246 administration or if there are subsequent deaths that are definitely or probably related to study treatment.

10. DOSING DELAYS/MODIFICATIONS

1. Dose modification and dose delay

For patients who do not tolerate the protocol-specified dosing schedule, dose adjustments are permitted in order to allow the patient to continue the study treatment. All dose modifications, interruptions or discontinuations must be based on the worst preceding toxicity as graded by the

NCI Clinical Toxicity Criteria (NCI-CTCAE version 4.03). Once a dose has been reduced during a treatment cycle, re-escalation will not be permitted during any subsequent cycle (with exception of CNS events, see 10.2). If the administration of APR-246 is interrupted for reasons other than toxicity, then treatment with the respective study drug may be resumed at the same dose. The same provision applies if the patient experienced an unacceptable toxicity not specifically described in Table 8 provided that this toxicity resolved to \leq CTCAE grade 1, unless otherwise specified.

2. Treatment of adverse events of the CNS related to APR-246

If a patient reports any clinical adverse event of any grade during the administration period of APR-246 that could be considered to originate from the central nervous system (e.g., dizziness, vertigo, nausea) then the following medications may be used (Table 6). Prochlorperazine is not required to be taken at any point but is per discretion of the treating physician.

Table 6. Adjuvant Medications for use with APR-246

Indication	Supportive Measure
Central Nervous System (CNS) symptoms (Treatment and Prevention)	Prochlorperazine 10 mg orally tid as needed Start Day -1 prior to APR-246 administration
Persistent CNS symptoms	Diphenhydramine 50 mg IV (or similar anti-histamine)

Prochlorperazine 10 mg orally tid (three times daily) to continue until end of Day 4 of the cycle. When used prophylactically for future treatment, start the day prior to Day 1 administration of APR-246. If during the infusion the patient continues to remain symptomatic, intravenous administration of diphenhydramine 50 mg (or similar anti-histamine) should be considered. If prophylactic prochlorperazine results in \leq grade 1 CNS toxicity on subsequent doses, re-escalation to previous dose level can occur with the next cycle at the discretion of the study investigator.

3. Treatment interruption and treatment discontinuation

Patients requiring a dose delay of > 28 days must be permanently discontinued from study drug. Following 4 cycles of therapy for responding patients (i.e. CR, PR, HI, or marrow CR), treatment with APR-246 and azacitidine can be delayed per the study investigator for up to 14 days to allow for count recovery or at investigator discretion post discussion with Moffitt PI. Non-hematologic grade 4 treatment related adverse events will lead to permanent discontinuation, irrespective of recovery time, unless otherwise specified. Exceptions would include nausea/vomiting/diarrhea which can be controlled by medications and/or asymptomatic electrolyte imbalances which can be corrected. In addition, in most instances, patients that experience a prolonged treatment interruption because of an adverse event and/or a grade 3 adverse event will decrease the dose of study drug after their recovery (see specific tables for dose adjustment guidelines). Furthermore, patients requiring >1 dose reduction for APR-246 will be permanently discontinued from study drug. Patients who permanently discontinue all study drugs should have follow-up within 30 days after discontinuation of all study treatment or resolution of the AE to \leq grade 1, whichever occurs first, that includes all study assessments appropriate to monitor the event.

4. DLT Definition

Patients will be evaluated for DLTs during the lead-in phase and first cycle of combination therapy, i.e., 6 weeks for purpose of deciding the dose for next cohort (see Table 1) but DLTs will continue to be evaluated and reported through all cycles on study. DLT is defined as follows based on the CTCAE v 4.03:

- Treatment related non-hematological CTCAE grade 3-4 toxicity that lead to dose modification or withdrawal.
- Absolute neutrophil count (ANC) not recovering to $>500/\mu\text{L}$ by day 42 of a cycle in the absence of active leukemia/myelodysplasia will be considered a DLT.
- Grade 3 metabolic/electrolyte abnormalities that are not clinically significant, and are adequately controlled within 72 hours are not to be considered DLT.
- Grade 3 nausea/vomiting/diarrhea or CNS toxicity that does not resolve within 28 days despite treatment interruption and maximum medical therapy will be considered a DLT.

5. Criteria for APR-246 dose modifications (Phase 2)

For patients who do not tolerate APR-246 initial dosing schedule, dose adjustment is permitted in order to allow the patient to continue on study drug. In general, doses should not be reduced

for grade 1 toxicities or grade 2 toxicities with resolution on dose interruption (see Table 8), but treatment to control symptoms should be provided as appropriate. The starting dose level of APR-246 will be based on the recommended phase 2 dose (RP2D) upon completion of the phase 1 component of the trial (see Table 5). If dose level 3 (i.e. 100mg/kg LBW) is the RP2D based on the phase 1b part of the trial, the dosing will be changed to an equivalent fixed dose regimen of 4500mg/patient. For each patient, a maximum of 2 dose reductions of APR-246 (as outlined in Table 7) will be allowed. Patients requiring an additional dose reduction will be discontinued from treatment with APR-246. Patients whose treatment is interrupted or permanently discontinued due to an adverse event or clinically significant laboratory value must be followed up within 30 days, or resolution of the AE to \leq grade 1, whichever occurs first, that includes all study assessments appropriate to monitor the event.

Table 7 Dose reduction steps for APR-246 (Phase 2 only)

APR-246 dose levels and dose reduction*	
Starting dose level	RP2D days 1-4 of each cycle
Dose level – 1	RP2D-500mg fixed dose days 1-4 of each cycle**
Dose level – 2	RP2D-1000mg fixed dose days 1-4 of each cycle**

*Dose reduction should be based on the worst preceding toxicity.
 ** = If a dose reduction below dose level –2 is required, the patient should be permanently discontinued from APR-246

Guidelines for dose modification and dose interruption for toxicities suspected to be related to APR-246 are described in Table 8.

Table 8 APR-246 – recommended dose modifications and criteria for treatment interruption and re-initiation with treatment-related adverse events

These changes must be recorded on the Dosage Administration Record CRF.

Worst toxicity (CTCAE 4.03 Grade)**	Dose Modifications for APR-246
HEMATOLOGICAL (only applicable for patients with normal baseline absolute neutrophil count (ANC) and platelets)	
Neutropenia (ANC)	
Severe Febrile neutropenia	Omit dose until resolved, then ↓ 1 dose level

Worst toxicity (CTCAE 4.03 Grade)**	Dose Modifications for APR-246
(ANC < 0.5 x 10 ⁹ /L, temperature of ≥ 38 °C and ICU admission)	
Thrombocytopenia	
Grade 4 (PLT < 25 x 10 ⁹ /L) AND major bleeding event	Permanently discontinue patient from APR-246
RENAL	
Serum creatinine	
Grade 1 (< 2 x ULN)	Maintain dose level
Grade 2 (2 – 3 x ULN)	Omit dose until resolved to ≤ grade 1, then: If resolved in ≤ 7 days, then maintain dose level If resolved in > 7 days, then ↓ 1 dose level
Grade 3 (> 3.0 – 6.0 x ULN)	If resolved in ≤ 7 days, then ↓ 1 dose level If resolved in > 7 days, discontinue patient from APR-246
Grade 4 (> 6.0 x ULN)	Permanently discontinue patient from APR-246
HEPATIC	
Bilirubin	
(*for patients with Gilbert Syndrome, these dose modifications apply to changes in direct bilirubin only) will be fractionated if elevated	
Grade 1 (> ULN - 1.5 x ULN)	Maintain dose level with LFTs* monitored as per protocol
Grade 2 (> 1.5 - 3.0 x ULN) with ALT or AST ≤ 3.0 x ULN	Omit dose until resolved to ≤ Grade 1, then: If resolved in ≤ 7 days, then maintain dose level If resolved in > 7 days, then ↓ 1 dose level
Grade 3 (> 3.0 - 10.0 x ULN) with ALT or AST ≤ 3.0 x ULN	Omit dose until resolved to ≤ Grade 1, then: If resolved in ≤ 7 days, ↓ 1 dose level If resolved in > 7 days, discontinue patient from APR-246
Grade 4 (> 10.0 x ULN)	Permanently discontinue patient from APR-246
AST or ALT	
Grade 1 (> ULN – 3.0 x ULN)	Maintain dose level with LFTs* monitored per protocol
Grade 2 (> 3.0 - 5.0 x ULN) without total bilirubin elevation to > 2.0 x ULN	Omit dose until resolved to ≤ Grade 1, then If resolved in ≤ 7 days, then maintain dose level If resolved in > 7 days, then ↓ 1 dose level
Grade 3 (> 5.0 - 20.0 x ULN) without total bilirubin elevation to > 2.0 x ULN	Omit dose until resolved to ≤ Grade 1, then If resolved in ≤ 7 days, then maintain dose level If resolved in > 7 days, then ↓ 1 dose level

Worst toxicity (CTCAE 4.03 Grade)**	Dose Modifications for APR-246
Grade 4 (> 20.0 x ULN) without bilirubin elevation to > 2.0 x ULN	Permanently discontinue patient from APR-246
*(LFTs include albumin, ALT, AST, total bilirubin (fractionated if total bilirubin > 2.0 x ULN), alkaline phosphatase.	
CNS – dizziness, dyskinesia and ataxia	
Grade 1	Maintain dose level
Grade 2	If resolved with medical therapy (e.g., prochlorperazine or antihistamines), continue same dose level If not resolved despite treatment interruption and maximal medical therapy, stop infusion and ↓ 1 dose level for subsequent dose
Grade 3	If resolved with medical therapy (e.g., prochlorperazine or antihistamines), continue same dose level If not resolved despite treatment interruption and maximal medical therapy, stop infusion and ↓ 1 dose level for subsequent dose
Grade 4	Permanently discontinue patient from APR-246.
Infusion Related Reaction	
Grade 1	Maintain dose level.
Grade 2	Maintain dose level; Symptomatic management (e.g., antihistamines, corticosteroids, narcotics, IV fluids)
Grade 3	If resolved in < 4 hours with treatment interruption and medical therapy (e.g., antihistamines, corticosteroids, narcotics, IV fluids), continue same dose level and rate. If not resolved in < 4 hours despite treatment interruption and maximal medical therapy, stop infusion and ↓ 1 dose level for subsequent dose
Grade 4	Permanently discontinue patient from APR-246.
Nausea/Vomiting/Diarrhea	
Grade 1	Maintain dose level
Grade 2	If resolved, then maintain dose level If not resolved despite maximal medical therapy, then ↓ 1 dose level
Grade 3	If resolved, then maintain dose level If not resolved despite maximal medical therapy, then ↓ 1 dose level
Grade 4	Permanently discontinue patient from APR-246

Worst toxicity (CTCAE 4.03 Grade)**	Dose Modifications for APR-246
QTc Prolongation	
Grade 1	Maintain dose level
Grade 2	Correct electrolytes and discontinue concomitant medications that cause QTc prolongation. If resolved, then maintain dose level. If not resolved, then ↓ 1 dose level
Grade 3	Omit dose until resolved to ≤ Grade 1, If resolved, then ↓ 1 dose level If not resolved despite correction of electrolytes and discontinuation of concomitant medications that cause QTc prolongation, permanently discontinue maximal medical therapy
Grade 4	Permanently discontinue patient from APR-246
** Common Terminology Criteria for Adverse Events (CTCAE) version 4.03. These changes must be recorded on the Dosage Administration Record eCRF.	

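### Section 10.3 and Table 8 give opposite instructions for medication-controlled grade 4 nausea, vomiting or diarrhea, and the conflict may also change DLT status

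*Combined protocol and SAP*

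**What the plan says.** **Section 10.3 (treatment interruption and discontinuation).** The general rule is: "Non-hematologic grade 4 treatment related adverse events will lead to permanent discontinuation, irrespective of recovery time, unless otherwise specified". The next sentence carves out two kinds of event. The first is the one at issue here: "Exceptions would include nausea/vomiting/diarrhea which can be controlled by medications". The second is correctable electrolyte disturbance without symptoms. Section 10.3 carries no phase limit.

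**Table 8 (Section 10.5), nausea/vomiting/diarrhea.** The grade 2 and grade 3 rows depend on the outcome of treatment. If the event resolves, the dose level is kept; otherwise, "If not resolved despite maximal medical therapy, then ↓ 1 dose level". The grade 4 row has no such branch: "Permanently discontinue patient from APR-246".

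**DLT definition (Section 10.4, repeated in the synopsis).** The first criterion is: "Treatment related non-hematological CTCAE grade 3-4 toxicity that lead to dose modification or withdrawal". The criterion specific to gastrointestinal and CNS events begins "Grade 3 nausea/vomiting/diarrhea or CNS toxicity that does not resolve within 28 days despite" and goes on to require that interruption and full medical treatment have failed. It does not mention grade 4. DLTs in the lead-in plus cycle 1 (6 weeks) drive escalation, but "DLTs will continue to be evaluated and reported through all cycles on study".

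**Escalation rule (Section 6 and synopsis).** With no DLT in a cohort, the next level opens. With 1 DLT in 3, up to 3 more patients are added. With 1 in 6, the next level opens. With 2 in 6, escalation ends and the MTD is the level below.

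**The concern.** A patient with treatment-related grade 4 vomiting that medication controls falls under both texts. Section 10.3 exempts the patient from permanent discontinuation; Table 8 takes the patient off APR-246. The trial is multi-institutional, so different sites could handle the same event differently with no protocol deviation at either.

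There is a second-order effect. The first DLT criterion is defined by how the event is managed, not by grade alone. Where the protocol gives two management instructions for one event, it can also give two DLT classifications. DLTs are the Phase 1b primary endpoint (Section 3.1.1), so it matters whether and when the conflict reaches dose escalation.

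**Working it through.** No figure in the plan is at stake, so the main check sets the texts side by side.

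**Step 1: action for a medication-controlled, treatment-related grade 4 event**

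| Source | Instruction |
|---|---|
| Section 10.3, general rule | permanent discontinuation |
| Section 10.3, exception | exempt from that rule |
| Table 8, grade 4 row | permanent discontinuation, unconditional |

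The qualifier in the general rule about matters specified elsewhere does not settle this, because both the exception and the table specify, and they disagree. The grade 2 and 3 rows carry a treatment-outcome condition and the grade 4 row does not, so a reader cannot assume an unstated condition there.

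**Step 2: DLT status of the same event**

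| Handling | First DLT criterion | Gastrointestinal criterion | DLT? |
|---|---|---|---|
| Withdrawn, per Table 8 | met (withdrawal) | grade 3 only | yes |
| Kept on under 10.3, dose reduced | met (modification) | grade 3 only | yes |
| Kept on under 10.3, no modification | not met | grade 3 only | no |

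The classification differs between the two texts only when the third row would otherwise apply.

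**Step 3: phase**

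- Pointing to Phase 2 only: Table 8 sits in Section 10.5, whose heading names Phase 2. That section takes its starting dose from the RP2D, and its reduction ladder, Table 7, is labelled for Phase 2 alone.
- Pointing to wider use: Table 8 has no phase label of its own, and Section 10.1 refers to it without a phase limit.

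The scope is therefore unresolved.

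**Step 4: size if both conditions hold in Phase 1b**

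One reclassified patient changes 0/3 to 1/3 (escalate versus add up to 3 patients), or 1/6 = 16.7% to 2/6 = 33.3% (escalate versus stop).

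For illustration, let p be the per-patient DLT probability. Under the stated rule,

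P(escalate) = (1−p)³ + 3p(1−p)² × (1−p)³.

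At p = 0.20: 0.512 + 0.384 × 0.512 = 0.709. Suppose reclassified grade 4 events add q to a base rate from other causes. Both rates are assumptions; the documents give neither.

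| Base DLT rate | q = 0 | q = 2% | q = 5% | q = 10% |
|---|---|---|---|---|
| 10% | 0.906 | 0.871 | 0.814 | 0.709 |
| 15% | 0.814 | 0.773 | 0.709 | 0.600 |
| 20% | 0.709 | 0.665 | 0.600 | 0.494 |
| 25% | 0.600 | 0.557 | 0.494 | 0.396 |

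The chance of at least one such event in 6 patients is 1 − (1−q)⁶: 11.4% at q = 2%, 26.5% at 5% and 46.9% at 10%.

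**Step 5: Phase 2**

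The decision rules (6 of 24, then 14 of 45) count complete remissions, so the DLT label does not enter them. In Phase 2 the conflict bears on patient handling and, because DLTs are reported in all cycles, on DLT reporting.

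**The case against.** **Table 8 may be a Phase 2 table.** If so, only Section 10.3 governs a Phase 1b patient, and no escalation decision changes. A reader might infer from Section 10.4 that the contradiction necessarily reaches the Phase 1b primary endpoint. The Phase 2 heading of Section 10.5 prevents that conclusion. The unrestricted reference in Section 10.1 and the missing phase label keep the possibility open, so the most that can be said is that it may reach it.

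**The exception lifts discontinuation only.** A reader might also infer that following Section 10.3 means the event is not a DLT. The documents do not say so. Section 10.3 does not say that dosing continues unchanged. It goes on to say that a prolonged interruption or a grade 3 event usually leads to a lower dose. A reduction would make the event a DLT under the first criterion on either reading. This objection stands and limits the DLT effect.

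**Table 8 is advisory in tone.** Its title calls the modifications recommended, and the text introduces it as guidelines. A site could take the Section 10.3 exception as qualifying the table. That softens the clash but does not remove it: no sentence gives precedence, and Section 10.3 itself sends the reader to the tables for dose adjustment.

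**Frequency is unknown.** Section 10.2 names nausea, but only as an example of a possible CNS event of any grade. It is not evidence that medication-controlled grade 4 gastrointestinal events are common. The shifts in cohort counts are what any single DLT does in a 3+3 design; they show sensitivity, not likelihood.

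**Conclusion.** The textual conflict is certain: at least in Phase 2, one event carries opposite instructions and nothing ranks them. The DLT consequence is conditional. In Phase 1b it requires both that Table 8 applies there and that treatment under Section 10.3 would resume with no dose modification. If both hold, a single event is enough to turn escalation into cohort expansion or into stopping. With an assumed 20% base DLT rate and an assumed 2 to 10 percentage points of such events, the chance of escalating past a level falls from 0.709 to between 0.665 and 0.494. Those rates are not in the documents, so the range shows scale only. If either condition fails, the 3+3 decisions are unaffected, while the Phase 2 handling conflict remains.

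**What to change.** Reconcile Section 10.3, the grade 4 nausea/vomiting/diarrhea row of Table 8, and the DLT definition in Section 10.4 and the synopsis, so that a treatment-related grade 4 event of this kind has one stated action and one stated DLT classification. State whether Table 8 applies in Phase 1b. The content of the rule is for the clinical team to decide. The cost is amendment wording; sample size, decision boundaries and data collection do not change.
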